3. STUDY PROCEDURES

The study is divided in three distinct periods: screening (visit 1), enrollment and in-hospital period (visits 2 and 3), and follow-up period (visits 4 and 5).

3.1 Informed consent

The participant must personally sign and date the latest approved version of the informed consent form before any study specific procedures are performed.

Written and verbal versions of the Participant Information Sheet and Informed Consent will be presented to the participants detailing no less than: the exact nature of the study; the implications and constraints of the protocol; the known side effects and any risks involved in taking part. It will be clearly stated that the participant is free to withdraw from the study at any time for any reason without prejudice to future care, and with no obligation to give the reason for withdrawal.

The participant will be allowed as much time as wished to consider the information and the opportunity to question the Investigator, their general practitioner (**GP**) or other independent parties to decide whether they will participate in the study. Written informed consent will then be obtained by means of participant dated signature and dated signature of the person who presented and obtained the informed consent. The person who obtained the consent must be suitably qualified and experienced, and have been authorized to do so by Principal Investigator. A copy of the signed Informed Consent will be given to the participants. The original signed form will be retained at the study site.

3.2 Screening and eligibility assessment

Start of period: When a given patient is admitted to the hospital because unexplained COPD exacerbation.

End of period: Twenty-four hours after decision to admit to hospital.

Setting: Emergency Department.

e-CRF entries:

- Demographics: date of birth, gender
- Medical history
- Concomitant medication
- Physical examination: height, weight, heart rate, systolic blood pressure, temperature, respiratory rate, arterial oxyhemoglobin saturation
- Inclusion and exclusion criteria
- Laboratory tests: hemogram, biochemistry, and hemostasis
- Chest X-ray
- Informed consent

3.3 Enrollment and in-hospital period

Start of period: When a given patient is randomized.

End of period: When a given patient is discharged.

Setting: Hospital.

e-CRF entries:

- Randomization group: intervention or control group
- D-dimer test results (Intervention group)
- CT pulmonary angiogram result (Intervention group)
- Symptomatic new or recurrent VTE
- Death
- Primary cause of death
- Major bleeding

- Clinically relevant non-major bleeding
- Serious adverse events
- Treatment for COPD exacerbation
- Hospital discharge

At day 7, it will be recorded if the patient was discharged or not. Hospital discharge is defined as end of hospitalization or if the patient is transferred for long-term rehabilitation.

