Control group: All included patients will undergo standard clinical management of their exacerbations, as deemed appropriate by the attending physician.

Criteria for efficacy:

Primary end point

- Clinical composite endpoint of all-cause mortality or venous thromboembolism recurrence or need for COPD readmission within 90 days.

Secondary end points

- All-cause mortality within 90 days.
- Venous thromboembolic recurrence within 90 days.
- Need for COPD readmission within 90 days.
- Length of hospital stay.

Criteria for safety:

Primary end point

- Major bleeding within 90 days.

Secondary end points

- Clinically relevant non-major bleeding within 90 days.
- Serious adverse events within 90 days.

Statistical analysis: Intent-to-treat (ITT) analysis on superiority of an active strategy for the diagnosis and treatment of PE in patients with unexplained exacerbations of COPD requiring hospital admission.

Primary criteria

The primary ITT analysis on the primary end points will be carried out by a two-sided chi-square test on proportions. In addition, the 95% confidence interval on the relative risks will be presented.

Secondary efficacy criteria

The secondary ITT analysis on the secondary efficacy end points will be carried out by a two-sided chi-square test on proportions. In addition, the 95% confidence interval on the relative risks will be presented. The survival status during 90 days follow-up will be analyzed by showing Kaplan-Meier curves, and management differences will be compared by means of log-rank test.

Secondary safety analysis

Safety end points will be tabulated by management group. All (dichotomized) end points will be analyzed by chi-square test on proportions, and the 95% confidence interval on the relative risks will be presented. In addition, continuous safety monitoring will be done by the Data and Safety Monitoring Board.

Interim analysis

Interim analysis will be made by the Data Center after recruitment of 50% of the total number of patients. These analyses will be made in order to allow sample size reassessment or early stop of the trial for efficacy or futility.

TABLE OF CONTENTS	Page
ABBREVIATIONS	15
1. BACKGROUND	16
1.1 Study justification	16
1.2 Hypothesis	17
1.3 Objectives	17
2. METHODOLOGY	20
2.1 Design	20
2.2 Setting	20
2.3 Study subjects	21
2.4 Randomization	22
2.5 Study procedures	22
2.6 Criteria for termination of the trial	23
2.7 Definition of study end points	23
2.8 Surveillance and follow-up	28

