2.5.4 Secondary end points

Secondary efficacy end points

- Death from any cause within 90 days after enrollment.
- Nonfatal (recurrent) symptomatic VTE within 90 days after enrollment.
- Need of readmission for COPD exacerbation within 90 days after enrollment.
- Length of hospital stay.

Secondary safety end points

- Clinically relevant non-major bleeding within 90 days after enrollment.
- Serious adverse events (**SAE**) within 90 days after enrollment.

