means that a causal relationship between a study medication and an AE is at least a reasonable possibility, i.e., the relationship cannot be ruled out.

All cases judged by either the reporting medically qualified professional or the sponsor as having a reasonable suspected causal relationship to the study medication/procedure qualify as adverse reactions.

Serious adverse event: an event that fulfils one or more of the following criteria:

- Fatal.
- Immediately life-threatening.
- Results in persistent or significant disability/incapacity.
- Requires or prolongs in-patient hospitalization.
- Is a congenital anomaly/birth defect.
- Any other reason representing a significant hazard comparable to the criteria mentioned above.

Serious adverse reaction (SAR): an adverse event (expected or unexpected) that is both serious and, in the opinion of the reporting investigator, believed with reasonable probability to be due to one of the study treatments, based on the information provided.

Suspected unexpected serious adverse reaction (SUSAR): a serious adverse reaction, the nature or severity of which is not consistent with the applicable product information (e.g. Investigator's Brochure for an unapproved investigational product or summary of product characteristics for an approved product).

Length of hospital stay: defined as the interval (in days) from diagnosis of PE at the emergency department to discharge (i.e., date of discharge minus date of diagnosis).

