3.2 Missing data

Missing data won't be replaced, and analysis will be made on all evaluable patients. In addition, sensitivity analyses will be made on the primary and secondary end points using worst case and/or multiple imputations (see 3.5.3). Missing or incomplete data for survival analyses will be managed by censored data analyses.

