3.4 Baseline demographics and clinical characteristics

Baseline characteristics will be summarized by strategies on the randomized population. Only descriptive analyses will be provided (no inferential statistics).

Results will be presented as mean \pm one standard deviation if the variable follows a normal distribution and median [interquartile range] in case of other distribution. For the qualitative or categorical quantitative variables, results will be presented as numbers (proportions in %).

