3.5.2 Statistical analysis

The principal analysis of the primary and secondary end points will be performed on the evaluable patients from the randomized population with application of the intent-to-treat principle. In addition, safety analyses will be performed in the safety analysis set, which included all the patients in the control arm, and all the patients in the intervention arm who had received a D-dimer testing. The alpha level of the two-sided test is set to 0.05. The primary efficacy and safety end points will be analyzed by means of a two-sided chi-square test of proportions. The results for the primary end points will be also stratified according to center (4). Secondary end points will not be adjusted for multiplicity, and therefore these results should not be used to infer intervention

effects (5). Kaplan-Meier survival curves until 90 days after randomization will be compared with a log-rank test. For each end point, results will be presented as the relative risk (intervention:control) for percentages and difference (intervention-control) for means, and its 95% confidence interval (**CI**).

Cost-effectiveness will not be analyzed for the main presentation of the SLICE study but will be performed later as an ancillary study.

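### Length of hospital stay has no rule for death before discharge, and the synopsis and SAP give it different analyses, one of which cannot be applied to days

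*Protocol*

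**What the plan says.** **End point.** "Length of hospital stay" is listed among the secondary efficacy end points (SAP 2.5.4; Protocol 1.3 and 2.7). SAP 2.5.6 has it "defined as the interval (in days) from diagnosis of PE at the emergency department to discharge".

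**What counts as discharge.** Only Protocol 3.3 defines it: "Hospital discharge is defined as end of hospitalization or if the patient is transferred for long-term rehabilitation". The same section lists death and hospital discharge as separate e-CRF entries for the in-hospital period. Neither document says what length of stay a patient has who dies before leaving hospital.

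**Analysis.**
- Synopsis, secondary efficacy criteria: "The secondary ITT analysis on the secondary efficacy end points will be carried out by a two-sided chi-square test on proportions". Length of stay is not exempted and no cut-point is given.
- Protocol 2.10 names only the chi-square and Fisher exact tests.
- SAP 3.5.2 names the chi-square test for the primary end points. For all end points it says "results will be presented as the relative risk (intervention:control) for percentages and difference (intervention-control) for means", each with a 95% interval. It names no test for length of stay.
- SAP 3.4 allows "median [interquartile range] in case of other distribution", but for baseline tables only.
- The Kaplan-Meier and log-rank analysis is described as survival to day 90, not time to discharge.

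**Missing data.** SAP 3.2: "Missing data won't be replaced, and analysis will be made on all evaluable patients".

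**The concern.** Death ends a hospital admission. Without a rule for it, the analyst has two options:
- Use the date of death as the end of the stay. An early death then enters as a short stay, which for this end point looks like a good result.
- Treat the patient as having no discharge date, so that the patient leaves the evaluable set. The comparison is then among patients discharged alive, a group formed after randomization.

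The choice would be made at analysis, in an open-label trial whose primary composite includes death. The analyst would also find no consistent instruction on method, because one document prescribes a test that needs a proportion and the other prescribes a mean. What is at stake is the reading of one secondary efficacy end point, which is also to be reported in five sets of subgroups (SAP 3.6).

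**Working it through.** **The plan's own figure.** Neither document gives a sizing figure for length of stay. The only sample size is 355 per group for the primary composite (40% v 30%, two-sided 5%, 80% power). The unpooled formula gives (0.40×0.60 + 0.30×0.70) × (1.960 + 0.842)² / 0.10² = 354, and the pooled form gives 356. Power at 355 is 0.799. The figure reproduces, and 355 per arm is used below.

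**Inputs not in the documents (assumptions).** Mean stay of 9 days in patients discharged alive, in both arms; in-hospital death rate d; mean day of death D; log-normal stays.

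**1. Deaths counted as completed stays.**
Arm mean = (1 − d)×9 + d×D, so the difference between arms = −(d₁ − d₂)×(9 − D).

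| In-hospital deaths | D | Arm means (days) | Artefact |
|---|---|---|---|
| 5% v 3% | 4 | 0.95×9 + 0.05×4 = 8.75; 0.97×9 + 0.03×4 = 8.85 | −0.10 |
| 8% v 4% | 4 | 0.92×9 + 0.08×4 = 8.60; 0.96×9 + 0.04×4 = 8.80 | −0.20 |
| 4% v 2% | 3 to 6 | 8.76 v 8.88 to 8.88 v 8.94 | −0.12 to −0.06 |
| 10% v 5% | 3 to 6 | 8.40 v 8.70 to 8.70 v 8.85 | −0.30 to −0.15 |

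Equal rates and timing give zero. If deaths come later than day 9 on average, the sign reverses.

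**2. Deaths dropped as not evaluable.** Under the same model both arms have mean 9, so the artefact is zero. A bias would need a further assumption, namely that those who died would otherwise have had stays of a different length.

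**3. Comparison with precision.** For a log-normal with mean 9 and log-SD 0.8, SD = 9 × √(e^0.64 − 1) = 8.5. The 95% interval for the mean difference is ±1.96 × 8.52 × √(2/355) = ±1.25 days. The artefact in step 1 is well inside that.

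**4. Efficiency of the mean difference.** Simulation at 355 per arm, log-normal stays, no deaths, 15% shorter stay in one arm:

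| Log-SD | Power, means | Power, ranks |
|---|---|---|
| 0.5 | about 0.98 | about 0.99 |
| 0.8 | about 0.64 | about 0.75 |
| 0.9 | about 0.51 | about 0.64 |

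The type I error of the comparison of means stays close to 0.05. These powers compare means with ranks in the absence of deaths. They do not give the power of an analysis that ranks deaths as worst.

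**5. Synopsis against SAP.** A chi-square test needs a category for each patient. Protocol 3.3 does record whether the patient was discharged by day 7, but neither document makes that the length-of-stay end point. Under the same definition of discharge, a patient dead by day 7 would be just as ambiguous.

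**6. A side effect of dropping deaths.** SAP section 7 removes patients with missing secondary end points from the per-protocol set, in which SAP 3.5.3 repeats the primary analysis. If an in-hospital death left length of stay missing, the death could leave that set too. With a 40% composite rate and an assumed 3% to 8% of patients dying in hospital, all removed, the rate would become (40 − 3)/97 = 38.1% to (40 − 8)/92 = 34.8%. Whether this would happen is not stated.

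**The case against.** A reader might infer more than the documents support, and the case against doing so is strong on several counts.

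- **That the plan scores an in-hospital death as a short stay.** It does not say so. Separate e-CRF entries for death and discharge point, if anything, the other way, and the discharge sentence follows the day-7 item; it is not written as a scoring rule. A late death would not be short. What stands is that the handling is unspecified.
- **That either reading favours the arm with more early deaths.** Step 2 shows no artefact under exclusion without an extra assumption.
- **That skewness makes the mean difference invalid.** At this sample size it does not; it costs power, and at log-SD 0.5 almost none.
- **That SAP 3.4 contradicts SAP 3.5.2.** SAP 3.4 covers descriptive baseline tables only.
- **That the SAP already settles the chi-square issue.** In part: SAP 3.5.2 confines the chi-square test to the primary end points. The protocol text remains uncorrected, and the SAP names no test in its place.

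It is also fair that SAP 3.5.2 says secondary results should not be used to infer effects, and that a mortality imbalance would be visible because death is reported on its own. This limits the harm. It does not supply the missing rule, since an estimate with a 95% interval will still be reported.

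**Conclusion.** The point holds as a gap in the definition and an inconsistency in the analysis. The plan permits an in-hospital death to be scored as a completed stay or to be dropped. It assigns length of stay to a test that cannot use days in one document and to a mean difference in the other.

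The size is modest: about 0.1 to 0.2 day for 5% v 3% or 8% v 4% deaths (0.06 to 0.30 day over the wider range shown), against an interval of about ±1.25 days, and nothing if deaths are equal in rate and timing. The loss of power from using means runs from negligible to about 0.13, depending on skewness. All stay lengths, death rates and death days are assumptions, because the documents give none. The sample size and the ITT analysis of the primary composite are unaffected. This is worth correcting because the correction is cheap, not because the trial's main conclusion depends on it.

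**What to change.** - **SAP 2.5.6:** define the end of the stay as discharge alive (keeping the transfer-to-rehabilitation clause), and state that a patient who dies in hospital has not reached it. Align Protocol 3.3.
- **SAP 3.5.2:** treat in-hospital death as a competing event. Compare arms by cumulative incidence of discharge alive to day 90 and a rank-based test in which deaths take the worst rank. Report median [IQR], and keep the difference in means as a descriptive figure.
- **Synopsis:** take length of stay out of the chi-square sentence.
- **SAP section 7:** state that an in-hospital death does not count as missing length of stay.

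**Cost.** Wording only, since discharge and death are already e-CRF entries. The rule should be fixed before results by arm are seen. The downside is that the quantity estimated becomes time to discharge alive instead of mean days, so mortality enters a further end point; the retained mean difference softens this. The edit must be made together with a separate problem in SAP 2.5.6: the stay starts at PE diagnosis, a date that patients without PE do not have. Time to discharge alive needs a starting point that every randomized patient has.

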3.4 Subsequent assessments

Visits: Day 30 \pm 5 and Day 90 \pm 7.

Setting: Outpatient basis.

e-CRF entries:

- Recording of concomitant medications
- Symptomatic new or recurrent VTE
- Death
- Primary cause of death
- Major bleeding
- Clinically relevant non-major bleeding
- Serious adverse events
- Rehospitalization
- Primary cause of rehospitalization

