2. METHODOLOGY

2.1 Design

SLICE is an investigator-initiated, phase III, prospective, multicenter, randomized (1:1), open-label with blind end-point evaluation (**PROBE**), parallel-group trial comparing the efficacy and safety of an active search for PE (intervention group) with usual care (control group) in patients with unexplained exacerbations of COPD who require hospital admission (ClinicalTrials.gov identifier NCT02238639).

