2.7 Definition of study end points

Efficacy

The primary efficacy end point is the composite of death from any cause, non-fatal (recurrent) symptomatic VTE, or readmission for COPD exacerbation within 90 days after enrollment.

Confirmation of **(recurrent) symptomatic PE** requires symptoms of PE and a new or an extension of a previous intraluminal-filling defect in (sub)segmental or more proximal branches on PE-protocol chest CT pulmonary angiography.

Confirmation of **(recurrent) symptomatic DVT** requires symptoms of DVT and the following criteria: 1) In the absence of previous DVT investigations at baseline, a non-compressible venous segment on ultrasonography; 2) if there were previous DVT investigations at baseline, abnormal lower limb CCUS where compression had been normal; or, if previously non-compressible, a substantial increase (≥ 4 mm) in diameter of the thrombus during full compression.

Secondary efficacy end points include:

- Death from any cause within 90 days after enrollment.
- Nonfatal (recurrent) symptomatic VTE within 90 days after enrollment.
- Readmission for exacerbation of COPD within 90 days after enrollment.
- Length of hospital stay.

Safety

The primary safety end point is major bleeding within 90 days after enrollment.

Major bleeding is defined according to the guidelines of the International Society of Thrombosis and Haemostasis (20), as acute clinically overt bleeding associated with one or more among the following: a decrease in hemoglobin of 2 g/dL or more, a transfusion of two or more units of packed red blood cells, bleeding that occurs in at least one of the following critical sites (intracranial, intraspinal, intraocular, pericardial, intraarticular, intramuscular with compartment syndrome or retroperitoneal), bleeding that is fatal (defined as a bleeding event that the central independent committee adjudicate as the primary cause of death or contributing directly to death) and bleeding that necessitates surgical intervention.

Secondary safety end points include:

- Clinically relevant non-major bleeding within 90 days after enrollment.
- Serious adverse events (**SAE**) within 90 days after enrollment.

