2.5.2 Primary end points

Primary efficacy end point

- Clinical composite endpoint of death from any cause, non-fatal (recurrent) symptomatic VTE, or readmission for COPD exacerbation within 90 days after enrollment.

Primary safety end point

- Major bleeding within 90 days after enrollment.

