3.5.3 Sensitivity analyses

For the intention-to-treat population, sensitivity analyses will be made on the primary and secondary end points using worst case and/or multiple imputations. In addition, the analysis of the primary and secondary end points will be replicated in the per protocol population.

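### The primary composite counts only readmissions attributed to COPD exacerbation, and no planned analysis is independent of that attribution, which a PE diagnosis known mainly in one arm can influence

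*Protocol*

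**What the plan says.** Protocol 2.7 defines the primary end point: "The primary efficacy end point is the composite of death from any cause, non-fatal (recurrent) symptomatic VTE, or readmission for COPD exacerbation within 90 days". SAP 2.5.2 uses the same component ("non-fatal (recurrent) symptomatic VTE, or readmission for COPD exacerbation within 90 days after enrollment"). The only readmission end point among the secondary ones is also cause-specific: "Need of readmission for COPD exacerbation within 90 days after enrollment" (SAP 2.5.4).

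The follow-up e-CRF in Protocol 3.4 and 3.5 records any rehospitalization, together with "Primary cause of rehospitalization".

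The design is "open-label with blind end-point evaluation" (Protocol 2.1). D-dimer and CT angiography are protocol tests in the intervention group only (Study Plan; Protocol 2.5 and 3.3). A recurrent PE counts only if strict criteria are met: it "requires symptoms of PE and a new or an extension of a previous intraluminal-filling defect" (Protocol 2.7).

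A committee unaware of allocation adjudicates all suspected outcomes (Protocol 2.7) and confirms them (Protocol 4.3). Section 4.3 lists cause categories for deaths and none for readmissions. The one definition of COPD exacerbation is in the abbreviated protocol. It is broad, and it is written for the index admission.

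SAP 3.5.3 plans that "sensitivity analyses will be made on the primary and secondary end points using worst case and/or multiple imputations", and it repeats the analyses in the per-protocol population.

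**The concern.** Whether a readmission counts depends on the cause assigned to it, and the two arms do not hold the same information when that cause is assigned. Consider two patients with the same PE at the index admission, both readmitted with dyspnoea. In the intervention patient the PE is on record. The stay may be attributed to it, and if no new or extended defect is shown it is neither a VTE event nor a COPD readmission. In the control patient the PE was probably never looked for, and the stay can be recorded as a COPD exacerbation, which is an event. Readmissions for bleeding on anticoagulants also fall outside the efficacy composite.

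The stake is the interpretation of a positive result. Readmission is one of the three components of the primary end point. If a benefit appears, the plan contains no analysis that could show whether it survives when the cause of readmission is ignored, although the data for such an analysis are collected.

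**Working it through.** **The plan's own figure.** Inputs from the sample size text (Protocol 2.10, SAP 2.2): 40% versus 30%, 80% power, two-sided 5%. With pooled variance and no continuity correction,

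n = [1.96·√(2·0.35·0.65) + 0.8416·√(0.40·0.60 + 0.30·0.70)]² / 0.10² = 356 per arm, against the stated 355. Multiplying 355 by 1.05 gives 373; dividing it by 0.95 gives 374. The stated figures reproduce.

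**Label-bias model.** Suppose there is no true effect, 40% have the event in each arm, and 355 per arm are evaluable. The observed intervention rate falls by

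shift = (PE prevalence) × (share of PE patients readmitted) × (share of those readmissions given a non-COPD cause).

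- Prevalence: 3.3%, 16% and 25%, the three figures cited in Protocol 1.1.
- Readmitted share: 30%. This is an assumption; the documents give no figure.
- Relabelled share: 25% to 50%. This is also an assumption.

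**One case in full** (16% prevalence, half relabelled). Shift = 0.16 × 0.30 × 0.50 = 0.024, so the rates are 40.0% and 37.6%, with a mean of 38.8%. The standard error is √(2 × 0.388 × 0.612 / 355) = 0.0366, and the significance limit is 1.96 × 0.0366 = 0.0717.

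- Significant in favour of the intervention: Φ[(0.024 − 0.0717)/0.0366] = 9.6%.
- Significant against it: Φ[(−0.024 − 0.0717)/0.0366] = 0.4%.
- Two-sided total: 10.0%, against a nominal 5%.

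**All cases**

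| PE prevalence | Relabelled | Shift (points) | Patients of 355 | False benefit (nominal 2.5%) | Two-sided error (nominal 5%) |
|---|---|---|---|---|---|
| 3.3% | 25% | 0.25 | 0.9 | 2.9% | 5.1% |
| 3.3% | 50% | 0.50 | 1.8 | 3.4% | 5.2% |
| 16% | 25% | 1.20 | 4.3 | 5.1% | 6.2% |
| 16% | 50% | 2.40 | 8.5 | 9.6% | 10.0–10.1% |
| 25% | 25% | 1.88 | 6.7 | 7.4% | 8.0% |
| 25% | 50% | 3.75 | 13.3 | 17.6% | 17.7% |

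The false-benefit probability doubles to 5% at a shift of about 1.2 points, roughly 4 patients of 355. It reaches 10% at about 2.5 points, roughly 9 patients.

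For given inputs this is an upper bound. A relabelled patient may still count through death, a confirmed VTE or another COPD readmission by day 90.

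**Can a planned analysis detect it?**

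- Worst case and multiple imputation act on missing outcomes. A relabelled readmission is not missing; it is recorded as no event.
- The per-protocol analysis changes the patients and keeps the label.
- Hospitalization makes an event serious, so other readmissions enter the SAE end point, and bleeding readmissions enter the bleeding end points. In both they are mixed with other events, so neither yields an all-cause composite.

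In this model an all-cause composite cannot be moved by the label, so its false-benefit rate stays at 2.5%.

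**The case against.** The strongest answer is that the protocol already protects the end point. Adjudication is central and blind to allocation, and the e-CRF cause is not shown to be the final classification. A reader might infer that the adjudicators see notes naming the index PE; the documents do not say what they see. What stands is narrower: no masking of the index PE result is described, and no criteria for readmission cause are given. By contrast, Protocol 4.6 says that image readers are unaware of all clinical information.

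Second, the definition in the abbreviated protocol is wide enough to cover a dyspnoea readmission in a patient with known PE. If adjudicators apply it to readmissions, that stay is an event and the example fails. It cannot therefore be said that such stays will go uncounted. But the definition is written for the index admission, and nothing extends it to the end point.

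Third, a reader might conclude that the bias must favour the intervention. That is not supported. A known PE may prompt repeat imaging at readmission, and an apparent new or extended defect then adds a VTE event in that arm.

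Fourth, it would go too far to say that the readmission data are unused or that the sensitivity analyses deal only with missing data. The safety end points take in hospitalizations and bleeding, and SAP 3.5.3 includes a per-protocol repeat. Both remarks are correct, but neither provides a check on cause attribution.

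Finally, cause-specific readmission was a deliberate choice made by amendment. It is defensible, because all-cause readmission adds unrelated events. This argues for keeping the primary end point, and it leaves room for a supporting analysis beside it.

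**Conclusion.** The gap is real and inexpensive to close. The composite depends on a cause attribution for which no criteria are stated, in an open-label trial where the index PE result is known mainly in one arm, and every planned analysis of the composite keeps that attribution.

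The possible size depends mostly on PE prevalence. At 3.3% it is negligible. At 16% the two-sided error would be roughly 6–10%, and at 25% roughly 8–18%. Protocol 1.1 itself describes the 25% study as highly selected, and this trial excludes patients in whom PE was initially suspected, so the upper range should be read with caution. The 30% readmission share and the 25–50% relabelling share are assumptions, and the results are upper bounds for those inputs.

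The documents support the statement that cause attribution can produce a false benefit. They do not show that it will, or that the primary end point is wrongly chosen. This is a cheap improvement.

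**What to change.** Keep the primary end point and the sample size. In SAP 3.5.3:

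1. Pre-specify a supporting analysis of the primary composite with readmission for any cause in place of COPD readmission, using the same test and effect measure.
2. Tabulate all readmissions by arm and adjudicated cause.
3. State that a benefit seen with COPD-attributed readmission but not with all-cause readmission will be reported as dependent on cause attribution.

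The cost is one more analysis and one table on data already in the e-CRF. The all-cause version is noisier. With 355 per arm and a 10-point reduction, power is 79.9% at 40% versus 30%. It would be 77.7% at 45% versus 35% and 76.5% at 50% versus 40% (both higher control rates are assumed). That is acceptable for a supporting analysis and needs no more patients.
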